## 1.0 Study Summary

Study Title	Intervention to Improve Driving Practices Among High-Risk Teen Drivers
Study Design	Clinical Trial
Primary Objective	Determine the effects of the intervention on teens' risky driving events and unsafe driving behaviors.
Secondary Objective(s)	Determine the effects of the intervention on frequency and quality of parent-teen communications about safe driving practices, and traffic violation recidivism.
Research Intervention(s)/ Investigational Agent(s)	Driving feedback and parental communication training.
IND/IDE #	
Study Population	Youth aged 16-17 who committed a moving-related traffic violation and their parent/legal guardian ('parent') most involved with their driving.
Sample Size	240
Study Duration for individual participants	6 months
Study Specific Abbreviations/ Definitions	

## 2.0 Objectives

### 2.1 Describe the purpose, specific aims, or objectives.

Aim 1: Determine the effects of the intervention on teens' risky driving events and unsafe driving behaviors.

Aim 2: Determine the effects of the intervention on frequency and quality of parent-teen communications about safe driving practices.

Aim 3: Determine the effects of the intervention on teen traffic violation recidivism.

### 2.2 State the hypotheses to be tested.

Aim 1: Hypotheses: The two intervention groups will demonstrate significant reductions in risky driving events (hard braking, sudden acceleration, speeding) and unsafe driving behaviors (speeding, no seatbelt use, distracted driving) per 1,000 miles driven when compared to the control group; The Driving-Feedback plus Parent Communication Training group will have fewer risky driving events and unsafe driving behaviors than the Driving Feedback Only group.

Aim 2: Hypothesis: The Driving-Feedback plus Parent Communication Training group will engage in more frequent and higher quality parent-teen communications on safe-driving topics than the other two groups.

Aim 3: Hypothesis: The two intervention groups will demonstrate significant reductions in recidivism (subsequent traffic violations) when compared to the Control group; The

## PROTOCOL TITLE: Intervention to Improve Driving Practices Among High-Risk Teen Drivers

Driving-Feedback plus Parent Communication Training group will have lower rates of recidivism than the Driving Feedback Only group.

### 3.0 Background

#### 3.1 Describe the relevant prior experience and gaps in current knowledge.

Motor vehicle crashes are the leading cause of injury and death among teenagers in the US, and teen drivers have higher crash rates than drivers in any other age group.(1-6) Drivers who have committed a traffic violation are a particularly high-risk group for crashes, and crash-related injuries and deaths.(7-15) A growing number of technological advancements, ranging from in-vehicle devices to smartphone applications, are available to monitor and provide real-time and cumulative driving feedback to teens in order to reduce risky driving events and unsafe behaviors.(16-18) Evidence also suggests that parents play a vital role in their teens' safe driving behaviors by reinforcing safe driving habits and setting rules that limit driving in risky conditions. However, many parent-based interventions that utilize technology are limited to providing only feedback on driving, without actively instructing parents how to use the feedback. (17,19-21) Furthermore, very few teen driving interventions are designed specifically for parents of juvenile traffic offenders.

### **3.2 Describe any relevant preliminary data.**

We tested the feasibility of using in-vehicle driving feedback technology paired with parent communication training in a pilot in September 2017 at the Franklin County Juvenile Traffic Court. Teens and their parents were approached by a member of our research team following the teen's court hearing and invited to participate in the study. Interested parent-teen dyads were then screened for eligibility and then enrolled, if eligible. We enrolled 10 dyads (77% participation rate, 60% male, 90% first offense) within one week. Once the in-vehicle device and app were successfully installed/downloaded, we collected three weeks of driving data for each teen. Additionally, each parent was provided an individualized, virtual communication training (one week after enrollment) and a booster session (four weeks after enrollment) with a traffic safety communication specialist experienced in delivering the training. We instructed parents to review their teen's cumulative driving data and an online version of the parent-teen safe driving communication guide. Parents were also provided with a voice recorder to record and submit a 3-minute parent-teen conversation about safe driving following the initial parent communication training session. This recorded parent-teen conversation was used by the communication specialist to tailor the respective booster sessions and to assess intervention fidelity.

### **3.3 Provide the scientific or scholarly background for, rationale for, and significance of the research based on the existing literature and how will it add to existing knowledge.**

Our study will be the first to simultaneously evaluate the effectiveness of novel driving feedback technology augmented with parent communication training to improve safe driving practices among teens with traffic violations. Building on health-related behavioral change and health communication theories, this intervention trial will fill a critical gap in universal approaches by focusing on a high-risk population thus informing development of NIH-defined indicated level interventions. This study will have a significant impact on scientific knowledge by determining whether teen driving practices can be improved by driving feed-back technology and how parents can be assisted by the technology and training in reinforcing safe driving habits of teens following a traffic violation. This study will also provide evidence to inform traffic court judges' decisions regarding the type of driving safety program to which they refer teens. If our hypothesis is confirmed, we anticipate wide dissemination of our designed intervention throughout juvenile traffic offense systems, as well as the translation of this intervention to other high-risk teen driver populations and settings

## **4.0 Study Endpoints**

### **4.1 Describe the primary and secondary study endpoints.**

Determine the effects of the intervention on teens' risky driving events and unsafe driving behaviors.

Determine the effects of the intervention on frequency and quality of parent-teen communications about safe driving practices and traffic violation recidivism.

## 5.0 Study Intervention/Investigational Agent

### 5.1 Description: Describe the study intervention and/or investigational agent (e.g., drug, device) that is being evaluated.

**In-vehicle Driving Feedback Technology:** The Azūga™ in-vehicle driving feedback technology, which consists of a pager-sized device plugged into the vehicle's on-board diagnostic port (installed in the teen's car) and a smartphone app (downloaded on the teen's smartphone), will be installed/downloaded. Four types of feedback will be provided to intervention teens: 1) Direct audio feedback from the installed device; 2) Push notification on the phone screen when a trip ends; 3) Detailed cumulative driving data; and 4) A customized biweekly driving summary report.

**Parent Training:** An individualized virtual training in communication strategies about driving safety along with a booster session will be delivered by a traffic safety communication specialist to parents in the Driving Feedback plus Parent Communication Training group. Parents in this group will also be provided with access to their teen's driving data as well as an online parent-teen safe driving communication guide.

### 5.2 Device Handling: If the research involves drugs or device, describe your plans to store, handle, and administer those drugs or devices so that they will be used only on subjects and be used only by authorized investigators.

N/A

### 5.3 If the drug is investigational (has an IND) or the device has an IDE or a claim of abbreviated IDE (non-significant risk device), include the following information:

N/A

## 6.0 Procedures Involved\*

### 6.1 Describe and explain the study design.

This study is a randomized controlled trial (RCT) with one control and two intervention groups. Participants will include 240 dyads (80 per group), comprised of one teen driver (ages 16 or 17) who has committed a moving violation (e.g., speeding, failure to obey traffic signal) during the recruitment period and the parent/legal guardian ('parent') who is most involved with the teen's driving. According to Ohio law, when a teen driver under 18 years is cited by law enforcement for a traffic violation, the teen must appear in Juvenile Traffic Court within 2 weeks of the citation accompanied by a parent to confess or deny committing the traffic violation, providing our team with a good opportunity to recruit and enroll participants. After completing informed consent/assent and the baseline assessment, enrolled dyads will be randomly assigned into 1 of 3 groups using a stratified block randomization.

### 6.2 Provide a description of all research procedures being performed and when they are performed, including procedures being performed to monitor subjects for safety or minimize risks.

**In-person recruitment and enrollment:** If interested in participating in the study, participants can notify the Nationwide Children's Hospital (NCH) on-site research team after their court hearing. The NCH research team member will then talk more about the study, answer any questions, screen for eligibility, obtain written consent/assent, and schedule an in-person meeting at a place that is convenient for participants. Participants will be ensured that their refusal to participate in this study will not affect their driving privileges in any way, and that the judge and court official will be blinded to who participates in our research study. Subjects will then be randomized into one of the three study groups (described in detail later).

During the initial scheduled meeting, the NCH research team member will install the in-vehicle device in the teen's car and download the smartphone app on the teen's smartphone. The in-vehicle device will stay in the car for a period of six months. Teens in the Control Group will have the in-

## PROTOCOL TITLE: Intervention to Improve Driving Practices Among High-Risk Teen Drivers

vehicle device installed in their car, but all feedback features will be disabled. If they are randomized into the Feedback Only Group, researchers will provide instructions on how teens can review their driving data. If in the Device Feedback plus Parent Communication Training Group, the NCH research team member will help schedule a video call with a specialist at the University of Iowa within 2 weeks of enrollment for parents to receive communication training on how to motivate their teen to adopt safe driving habits. This video call will be up to 45 minutes long and will take place 2 weeks after enrollment. The research team will also help schedule a booster session 2 months of the initial training session. Additionally, the member of our research team will show the parent how to access their teen's cumulative driving data. The teens of the Feedback Only Group will also receive a biweekly cumulative driving report. Teens and parents of the Device Feedback Plus Parent Communication Training Group will also receive a biweekly cumulative driving report as well as parental progress completing the online safe driving communication guide. Furthermore, we will obtain information about the teen's car year, make, and model for all participants regardless of group assignment. This initial meeting should take approximately 30 minutes.

The research team will reach out to participants at 3 months post-enrollment to have them fill out an online survey and terminate the active intervention for the intervention groups (Groups 2 & 3). At the end of 6 months, the NCH research team member will meet with participants in-person to end enrollment, and to collect the in-vehicle device. Additionally, they will administer a final survey to participants. After completion of this survey, participation in this study will be complete.

Virtual recruitment and enrollment: Teen drivers that receive a citation will still come to the courthouse for their hearing. However, teens and parents that are interested in participating will be able to scan a QR code from a study flyer that is posted within the waiting room of the courthouse or receive the flyer with their final paperwork from the clerks. If the teen and parent are interested, they will scan the QR code which will direct them to our REDCap. On the REDCap they will complete the eligibility form. If they are eligible, it will alert the NCH research team. The NCH research team will then reach out to the teen and parent to confirm interest in the study and schedule them for the enrollment meeting. The NCH research team will send the consent form to the teen and parent at this time for them to review prior to the meeting.

During the enrollment meeting, the NCH research team will video conference with the teen and parent. The researcher will go through the consent form and answer any questions the teen or parent may have. Once the questions have been answered the teen and parent will be instructed to virtually sign the consent form. Once they have completed the consent and assent form, the researcher will then send other study documents to the teen and parent through REDCap to complete. Once they have completed those forms the researcher will describe the specific group activities the teen and parent will need to complete based on which group they are in for the study. At the end of the call, the researcher will schedule another call with the teen and parent for the installation of the study devices. Once the call has ended the researcher will send any documents the teen or parent requested (i.e., consent form) and the group activities sheet. The researcher will also ship the study devices within 24 hours of the initial call to the teen and parent. This call should take about 30 to 45 minutes.

This study will use Twilio, a third-party platform that is integrated with REDCap, to:  
Send SMS messages with survey links to a REDCap form:  
Bi-weekly REDCap surveys will be sent via text. The text message will not include PHI or PII. The text message will provide a link to the secure REDCap platform. The participant will click on the link and be directed to a secure REDCap platform to complete the weekly survey.

Send informational texts and notifications:

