**6.4 What data will be collected during the study and how that data will be obtained.**

1. Risky driving events (hard braking, sudden acceleration, speeding): will be collected among teens in all three groups using the Azūga™ in-vehicle device. The number and type of driving event, including hard braking ( $\leq -0.45$  g-force) sudden acceleration ( $> 0.35$  g-force), and speeding ( $>10$  miles over the posted speed limit), and speed  $>75$  mph will be automatically coded and counted in the system. The rates will be computed by dividing events by miles driven then multiplying by 1,000.
2. Unsafe driving behaviors: Using the Azūga™ in-vehicle device and smartphone app, we will collect data on teen's unsafe driving behaviors (e.g., speeding, no seatbelt use). The duration (e.g., miles driven) and type of driving behaviors, including speeding ( $>10$  miles over the posted speed limit), will be automatically coded and counted in the system. The proportions will be calculated by dividing by miles driven then multiplying by 1,000 (e.g., proportion of 1,000 miles in which speeding). In addition, surveys will collect self-reported distracted driving (e.g., calls made and received, texts sent and viewed while driving, searches for a webpage/app) and seatbelt use (since not all vehicle models are available via Azūga™ in-vehicle device).

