## PROTOCOL TITLE: Intervention to Improve Driving Practices Among High-Risk Teen Drivers

6-month follow-up. To compare the differences among the 3 groups, one-way ANOVAs will be used. To model the effects of the intervention on the rates of risky driving events per 1,000 miles driven, a Quasi-Poisson analysis for over-dispersed count data will be conducted, where 2 dummy variables indicating Groups 2 and 3 will be created as covariates to determine risk ratios of risky driving events among the 3 groups, adjusting for the other potential covariates.

For the primary outcome of unsafe driving behaviors (speeding, distracted driving, no seatbelt use), to model the effects of the intervention on the proportion of unsafe behaviors per 1,000 miles driven, Quasi-Poisson analysis for over-dispersed count data will be implemented, where two dummy variables indicating Groups 2 and 3 will be created as covariates to determine the risk ratios of unsafe driving behavior among the 3 groups, adjusting for the potential covariates described above. In addition, a secondary analysis of correlation coefficients will be conducted to ascertain if and how the risky driving events and unsafe driving behaviors are correlated and whether the correlations are different between the study groups. The potential covariates will be adjusted.

For the secondary outcome of frequency and quality of parent-teen communication about driving safety, to model the effects of the intervention on differences in frequency and quality of parent-teen communication among the 3 groups, an Analysis of covariance (ANCOVA) will be used for each outcome, adjusting for the potential covariates. In addition, the following secondary analyses will be performed: 1) Correlation analysis will be conducted to examine if and how frequency and quality of parent-teen communication are correlated; 2) Longitudinal data analyses using mixed-effect models will be performed to further ascertain if the parent training enhances parent-teen communication over time with a focus on how these measures change over time in Group 3; 3) We will conduct further analysis on risky driving events and unsafe driving behaviors using the Quasi-Poisson analysis by including the measures of frequency and quality of parent-teen communication as three additional covariates to evaluate the effects of parent-teen communication, adjusting for group differences.

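### The 3-month survey is completed online and the 6-month survey is given by staff in person, so Group 3 trends in self-rated outcomes cannot be separated from a change in survey setting

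*Combined protocol and SAP*

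**What the plan says.** Section 6.2 (in-person route) sets two follow-up contacts after enrolment, on the same schedule for all three groups. At 3 months the team will "reach out to participants at 3 months post-enrollment to have them fill out an online survey", and the active intervention ends at that contact. At 6 months a team member "will meet with participants in-person to end enrollment, and to collect the in-vehicle device", and "they will administer a final survey to participants".

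The virtual route in 6.2 relies on REDCap forms and states that "Bi-weekly REDCap surveys will be sent via text". It does not describe the 3- and 6-month surveys separately. The mode of the baseline assessment in the in-person route is not given.

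Section 6.4 shows what depends on survey answers:

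- Item 2: "surveys will collect self-reported distracted driving", together with seatbelt use, because the device cannot read it in every vehicle model.
- Item 3: dyads' ratings of communication frequency and success. Quality is also scored by two trained coders from recorded conversations.
- Item 6: Group 3 parents' ratings of use, helpfulness and mastery of the strategies, after training and at 3 and 6 months.

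By contrast, item 1 says risky driving events "will be collected among teens in all three groups using the Azūga™ in-vehicle device".

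Section 17.1 analyses communication mainly by a between-group ANCOVA. As a secondary analysis, "Longitudinal data analyses using mixed-effect models will be performed to further ascertain if the parent training enhances parent-teen communication over time", with the focus on Group 3. No term or sensitivity analysis for survey mode is mentioned.

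**The concern.** Answers about phone use at the wheel, seatbelts and the quality of family conversations may be more favourable when a member of the study team is present. If the setting changes between 3 and 6 months for everyone followed in person, a within-group change over that interval contains the setting effect as well as any real change.

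The active intervention also stops at 3 months. A shift toward favourable answers at 6 months could therefore look like a communication benefit that lasts, or grows, after the intervention ends. The analysis cannot correct for this later among these dyads, because setting and visit coincide exactly.

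**Working it through.** The plan gives no figure on this point, so the check is a comparison of the sections, some algebra and one illustration.

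**Step 1: what is known to change.** The 3-month survey is filled out online after the team makes contact. The 6-month survey is given by staff at a meeting. That second description fits an interview, a paper form or the same online form completed at the visit. Setting and staff presence change; a change of instrument is not established.

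**Step 2: within one arm.** Write the mean response in group g at month t as Y(g,t) = μ(g,t) + m(t), where m(t) is the effect of the survey setting at that visit. Then

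Y(g,6) − Y(g,3) = [μ(g,6) − μ(g,3)] + [m(6) − m(3)].

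Only the sum can be estimated. This applies to the Group 3 trend in self-rated communication. It also applies to the Group 3 engagement ratings, which have no comparison arm.

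**Step 3: between arms.** At one visit, Y(3,6) − Y(1,6) = μ(3,6) − μ(1,6), because m(6) cancels. For the arm-by-time contrast,

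[Y(3,6) − Y(3,3)] − [Y(1,6) − Y(1,3)] = [μ(3,6) − μ(3,3)] − [μ(1,6) − μ(1,3)],

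and m cancels again. If the effect depends on the arm, m(g,t), the 6-month contrast is biased by m(3,6) − m(1,6). The documents give no information on the size or sign of that difference.

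**Step 4: illustration for Step 2.** Assumptions: 74 Group 3 dyads (the per-group number in 17.1), all changing setting; no true change from month 3 to month 6; a two-sided 5% test of the paired change; within-dyad correlation r; setting effect d in SD units. The documents give neither r nor d.

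SE = √(2(1 − r)/74), which is 0.116 for r = 0.5 and 0.090 for r = 0.7. The chance of a significant change is P(|Z| > 1.96) with Z centred at d/SE:

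| d (SD) | r = 0.5 | r = 0.7 |
|---|---|---|
| 0.1 | 0.138 | 0.199 |
| 0.2 | 0.405 | 0.603 |
| 0.3 | 0.733 | 0.915 |

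If only half the dyads change setting, the average shift halves. An effect of 0.2 SD then behaves roughly like the 0.1 SD row, 14% to 20%.

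**The case against.** The strongest reply is that the trial's hypotheses and main models compare randomized groups, and all groups share one survey schedule. A common setting effect cancels in those comparisons, as Step 3 shows. This stands, and it limits the point to within-group trends unless the effect differs by arm.

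Several stronger readings are tempting, and the documents do not support them:

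- A reader might infer that trends in self-reported driving are distorted. Section 17.1 plans no trend model for distracted driving or seatbelt use; the longitudinal model covers communication only and is secondary.
- A reader might infer that Group 3 parents would be answering to their own coach. Section 6.2 places the training with a specialist at another institution, while the 6-month meeting is with the hospital's research team. What remains is that the hospital team gives the group-specific instructions and schedules the training, and that only court personnel are described as blinded (6.2, 11.1, 13.1).
- A reader might take the table as an estimate of error. Its inputs are assumed, it treats every Group 3 dyad as changing setting although the virtual route's share and follow-up mode are unknown, and 17.1 does not specify a paired month-3-to-6 test.

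It is also fair to say that collecting the survey at the device-return visit protects completion. That benefit is worth keeping.

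**Conclusion.** The point holds in a limited form and is minor. For dyads followed as section 6.2 describes, the Group 3 change over time in self-rated communication and in training engagement cannot be separated from the change in setting and staff presence.

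Randomized contrasts, including those on self-reported distracted driving and seatbelt use at 6 months, are biased only if the setting effect differs by arm. Nothing rules this out, since no section states that the staff member is blind to group, but its size is unknown. Device-recorded events, including the outcome that set the sample size, and coder-scored conversations do not depend on survey mode.

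The illustrative range, from 14% at 0.1 SD with r = 0.5 to 92% at 0.3 SD with r = 0.7, rests wholly on the stated assumptions. It shows only that a modest setting effect could matter for a conclusion drawn from Group 3 alone.

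**What to change.** In 6.2, state that the baseline, 3-month and 6-month surveys use the same self-completed REDCap form in both enrolment routes. Teen and parent complete it separately, and staff do not read out questions or view answers. Send the 6-month link before the device-collection meeting. If it is still outstanding, allow private self-completion at that meeting. Record where each survey was completed, since late responders may still answer with staff nearby.

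In 17.1, base conclusions about communication over time on the arm-by-time contrast rather than on Group 3 alone. The engagement ratings have no comparison arm, so the common form is their main protection.

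The cost is a few sentences, on a platform the protocol already uses. Completion at 6 months could fall slightly; the prompt at the meeting limits this.
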